**Table 12.1-3 Simulation Results Using a Conditional Power Threshold of 0.0001%**

True HR	Chance (%) of Hitting Boundary A or B	Chance (%) of Hitting Boundary C (No Difference)	Chance (%) of Declaring Futility Before Analysis 18	Chance (%) of Declaring Futility at		
				Analysis 15	Analysis 16	Analysis 17
1.54	98.8	1.1	0.09	0.02	0.03	0.04
1.43	93.6	5.5	0.8	0.2	0.3	0.4
1.33	80.0	15.7	4.3	0.9	1.7	1.7
1.25	58.2	28.1	13.7	2.8	5.7	5.1
1.11	17.4	33.8	48.8	8.8	21.9	18.1
1.00	5.0	30.9	64.2	9.0	27.3	27.9
0.90	17.4	44.4	38.2	3.5	13.5	21.2
0.80	58.2	34.0	7.9	0.4	2.0	5.4
0.75	80.0	18.0	2.1	0.07	0.4	1.6
0.70	93.6	6.1	0.3	0.009	0.06	0.3
0.65	98.8	1.2	0.03	0.0003	0.004	0.02

The timing of these futility analyses will coincide with the scheduled interim analyses for efficacy, starting with Analysis 14 (projected at month 67; see Computations for Sample Size Expected to Generate 454 Events). This was selected because in none of the one million simulations was futility declared before Analysis 15.

Another adaptive design feature that will be used is sample size re-estimation.

Deviations from our assumed enrollment, withdrawal, and event rates could result in an overly lengthy trial (in calendar time). Current projections are to observe 454 events in 79 months. These projections will be updated as the trial nears full enrollment (1800 patients), and enrollment may be extended if needed to complete the trial on-time.

Because this is an event-driven trial, altering the total sample size is acceptable as long as 454 events could still eventually be observed. None of the other design features (total number of events, alpha-spending and power-accumulating functions) will be adaptively re-estimated or changed after the trial commences. To prevent bias, the decision to extend enrollment will be based only on overall (without regard to treatment group)

enrollment, withdrawal, and event rates. If this decision is required, it will essentially be a choice between enrolling additional patients to complete the study sooner or following 1800 patients longer.

All interim analyses (efficacy, futility, sample size re-estimation) will be performed by the unblinded statistician, who will serve as a liaison to the DSMB. The decision to terminate the trial due to efficacy or futility rests with the DSMB. It is the sponsor's decision whether to increase total enrollment.

If recruitment is faster than in (1), it should be ended before 48 months with a smaller total n, for otherwise the average follow-up may be too short. Also, a greater or lesser event rate will prolong or shorten the duration, as illustrated in **Table 12.1-4**.

**Table 12.1-4: Characteristics of the Study Design**

True HR	Power (in %)	Expected Trial Duration (Months)		
		20% Event Rate	25% Event Rate	30% Event Rate
1.00	5	83	71	64
0.80	58	80	69	62
0.75	80	71	62	56
0.70	94	65	57	52
0.65	99	60	53	49

Any slower rate of recruitment or lesser total recruitment will prolong the duration of the trial, about one month additionally for each two months delay in reaching target enrollment. Alternative scenarios for the estimate of the duration of the trial are demonstrated below: 1) assuming a uniform, faster enrollment rate of 45 ppm for the duration of the trial (1800 pts in 40 months), shortening the trial by 7 months (Table 12.1-5); 2) assuming a steady, slower enrollment rate of 30 ppm for the duration of the trial (1800 pts in 60 months), lengthening the trial by 3 months (Table 12.1-6).

Alternative Scenarios:

**Table 12.1-5: Assuming 45 ppm throughout (1800 pts in 40 months)**

True HR	Power (in %)	Expected Trial Duration (Months)		
		20% Event Rate	25% Event Rate	30% Event Rate
1.00	5	76	64	57
0.80	58	73	62	55
0.75	80	64	55	49
0.70	94	58	50	45
0.65	99	53	46	42

**Table 12.1-6: Assuming 30 ppm throughout (1800 pts in 60 months)**

True HR	Power (in %)	Expected Trial Duration (Months)		
		20% Event Rate	25% Event Rate	30% Event Rate
1.00	5	86	75	68
0.80	58	83	72	65
0.75	80	74	65	60
0.70	94	69	61	56
0.65	99	63	56	52

## 12.2. General Statistical Methods

### 12.2.1. Analysis Sets

All analyses will be carried out according to the intention-to-treat principle. All subjects randomized in the study will be included in the analysis.

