Additional Objectives	In all randomized subjects the following analyses will be performed: 
 
• All-cause mortality and sudden cardiac death in various subgroups including sex, race, age continuous and dichotomized at 75 years, duration of diabetes, presence vs. absence of insulin therapy, HbA1c dichotomized at 8%, LVEF continuous and dichotomized at 40%, and other relevant subgroups
 
• Healthcare utilization assessed through adverse event reporting
 

Additional Pre-Specified Analyses	In subjects randomized to S-ICD the following analyses will be performed: 
 
• Frequency and outcomes of S-ICD Inappropriate Shocks
 
• Frequency and outcomes of S-ICD treated ventricular tachycardia (VT) and ventricular fibrillation (VF)
 
• Frequency and outcomes of S-ICD device complications, including but not limited to: infection, device malfunction and electrode movement
 

Method of Assigning Patients to Treatment	Subjects will be randomized 2:1 (S-ICD:CMT). Randomization will occur electronically using the clinical data collection system.
Follow-up Schedule	
 
• Screening and Consent
 
• Baseline data collection
 
• Implant procedure (device subjects only)
 
• 1 month visit (in-clinic visit for S-ICD subjects and phone contact for CMT subjects)
 
• 6 month phone contact (conduct annually thereafter at months 18, 30, 42, etc.)
 
• 12 month visit (conduct annually thereafter at months 24, 36, 48, etc.) 
 
○ S-ICD Arm 12 Month in-clinic follow-up
 
○ CMT Arm 12 Month phone follow-up
 
 
 

Study Duration	The study is expected to enroll over a 48 month period with an average of 2.6 years of follow-up. Note: the length of the study is based on the accumulation of endpoint events and the hazard ratio.
Eligibility Criteria	Note: The most recent evaluations, measurements or test results in the medical record must be used to assess inclusion and exclusion criteria.

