### **10.5. *Implant Status and Classification***

For subjects randomized to the treatment (S-ICD) arm, the following additional definitions will be applied:

***Intent*** is defined as a subject randomized to the treatment (S-ICD) arm that does not undergo an S-ICD implant procedure.

***Attempted implant*** is defined as a subject randomized to the treatment (S-ICD) arm who undergoes an S-ICD implant procedure, but does not go on to receive the full S-ICD system within 30 calendar days of the initial implant procedure.

***Implant*** is defined as a subject randomized to the treatment (S-ICD) arm that undergoes an S-ICD implant procedure and is discharged with an S-ICD system.

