### 11.10.3. *PG/Electrode Explant without Replacement*

If the PG or electrode is explanted without replacement, an out-of-service device(s) form must be completed documenting details and rationale for explant (see section 11.10.4). Due to the intention to treat nature of the study, these subjects should still be followed to study completion.

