#### **12.3.1. Other Objectives/Measurements**

The secondary objective of the study will evaluate the effects of the S-ICD on all-cause mortality in various subgroups and on sudden cardiac death. Sudden cardiac death will be analyzed using methods similar to those for all-cause mortality, except that they will be performed without adjustment for the sequential design. Sudden cardiac death events in the study will be independently adjudicated by the Mortality Events Committee using the Hinkle-Thaler criteria (see Appendix 28.4).

The pre-specified subgroups include but are not limited to: gender, race, age continuous and dichotomized at 75 years, duration of diabetes, presence versus absence of insulin therapy, HbA1c < 8% or ≥ 8%, LVEF continuous and dichotomized at 40%, MADIT II risk score subgroups. For each subgroup analysis, the Cox proportional-hazards regression analysis will be used to evaluate differences between subgroups in the hazard ratios (S-ICD vs. CMT). The baseline covariate or stratum and its interaction with treatment group will be added to the regression model and a test for significant interaction carried out. Each analysis will be stratified by enrolling site, where appropriate. These analyses will be done without

adjustment for the sequential design. Subgroup analyses are further described in section 12.3.3.

Pre-specified tertiary analyses include the following:

1. Frequency and outcomes of S-ICD treated episodes of ventricular tachycardia (VT) and ventricular fibrillation (VF).
2. Frequency and outcomes of S-ICD inappropriate shocks.
3. Frequency of S-ICD device complications, including but not limited to: infection, device malfunction and electrode movement.
4. Healthcare utilization assessed through adverse event reporting.

Tertiary analyses will be descriptive and exploratory. Detailed statistical methods for these outcomes will be presented in a Statistical Analysis Plan (SAP) prior to study termination.

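### As written, the device shock and complication analyses keep S-ICD-arm subjects who never receive a device in the denominator, so risk per recipient is understated, by an amount the documents do not fix.

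*Combined protocol and SAP*

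**What the plan says.** Section 12.2.1 is all the plan says on analysis sets: "All analyses will be carried out according to the intention-to-treat principle. All subjects randomized in the study will be included in the analysis". No safety, as-treated or implanted set appears elsewhere.

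The synopsis, under Additional Pre-Specified Analyses, gives the population for the device outcomes: "In subjects randomized to S-ICD the following analyses will be performed". Its list includes "Frequency and outcomes of S-ICD Inappropriate Shocks", treated VT and VF, and device complications. Section 12.3.1 repeats these items, for example "Frequency of S-ICD device complications, including but not limited to: infection, device malfunction and electrode movement", without naming a population. It adds that "Tertiary analyses will be descriptive and exploratory" and leaves the detailed methods to a SAP due before the study ends.

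Section 10.5 classifies subjects in the S-ICD arm. *Intent* "is defined as a subject randomized to the treatment (S-ICD) arm that does not undergo an S-ICD implant procedure". *Attempted implant* covers a subject who has the procedure "but does not go on to receive the full S-ICD system within 30 calendar days of the initial implant procedure". *Implant* requires the procedure and discharge with a system. Footnote 2 to that section dates the procedure from the giving of anaesthesia. No analysis refers to these classes. For devices explanted and not replaced, section 11.10.3 says: "Due to the intention to treat nature of the study, these subjects should still be followed to study completion".

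**The concern.** Intention to treat is the right rule for a mortality comparison, where it protects the randomized contrast. The device outcomes are not a contrast. They occur in one arm only and describe what happens to people who have the implant. A subject who never reaches the operating room cannot have an implant complication or a shock from the study device, but under the stated rule still counts in the denominator. The same applies to time after an explant without replacement. The error runs one way: it makes the device look safer per recipient than it is. A patient or physician considering a prophylactic implant would want the per-recipient figure.

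**Working it through.** **Inputs.** 1,800 subjects (synopsis) at 2:1 (section 12.1.1.2) gives 1,800 × 2/3 = 1,200 in the S-ICD arm. The documents state no expected device event rate and no expected share without an implant, so there is no figure of the plan's own to reproduce on this point. The mortality design does not enter.

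**Who can have which event.**

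| Class in section 10.5 | Procedural complication | Shock, treated episode, later device complication |
|---|---|---|
| Intent | no | no |
| Attempted implant | yes | only if a system is placed after the 30 days |
| Implant | yes | yes |

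Two different shares therefore matter:
- f_P = share of the arm with no implant procedure (Intent).
- f_S = share who never have a system in place. This includes Intent subjects and those Attempted implant subjects who are never implanted later, so f_S is at least f_P.

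**Formula.** With r the true proportion among those who can have the event, the proportion over all randomized to S-ICD is r × (1 − f). The relative understatement is f, with f = f_P for procedural complications and f = f_S for the other device outcomes.

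**Numbers.** The values of f and r are assumptions.

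| f | Recipients of 1,200 | Events at r = 10.0% | Shown for r = 10.0% | Shown for r = 5.00% | Factor to recover r, 1/(1 − f) |
|---|---|---|---|---|---|
| 1% | 1,188 | 118.8 | 9.9% | 4.95% | 1.01 |
| 2% | 1,176 | 117.6 | 9.8% | 4.90% | 1.02 |
| 5% | 1,140 | 114.0 | 9.5% | 4.75% | 1.05 |
| 10% | 1,080 | 108.0 | 9.0% | 4.50% | 1.11 |

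The understatement is zero only if every subject in the arm is exposed.

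**Time at risk.** If rates are expressed per follow-up time, time without a device is also counted:
- Implantation may come up to 14 days after randomization (section 11.6.1). Against the projected mean follow-up of 2.6 years that is at most 14 / (2.6 × 365) = 1.5% of a compliant subject's time.
- Time after explant is added for subjects followed under section 11.10.3. The documents do not give its size.
- Subjects who accept only telephone contact are not withdrawn (section 11.11.1). Device episodes come from programmer printouts (Tables 11.7-1 and 11.9.2-1), and at the six-month contact only if chart review yields them (Table 11.8-1). Some of the counted time is therefore time in which an episode could occur and not be captured.

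**Scale.** The 95% sampling margin for 10% of 1,200 is 1.96 × √(0.10 × 0.90 / 1,200) = 1.7 percentage points, larger than every shift in the table.

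**The case against.** The best reply is that the denominator is not yet settled. The plan speaks of frequency, which could be a count, a proportion or a rate per device-time. Section 12.3.1 leaves detailed methods to a SAP, and denominator and exposure time are such details. Section 12.2.1 cannot apply literally to device outcomes, since it would bring in control subjects. The synopsis heading may be meant only to name the arm.

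The affected share may also be small. Subjects are randomized only after passing the S-ICD screening ECG (section 11.4) and after exclusion of device contraindications (Table 9.3-1), and implantation is due within 14 days. Device and procedure events are reportable one by one (section 20.1), the sponsor reviews aggregate adverse event rates (section 22.1), and implant status is recorded, so a per-recipient rate can be recomputed. The rate over all randomized is also a valid estimate for the strategy of assigning an S-ICD.

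Much of this stands: the analyses are descriptive, the size is unknown, and the SAP could still set a better denominator. Three things do not follow. The deferral of methods reserves no exception to the stated population, and the only population the plan names is the randomized arm. The SAP is due only before study termination, so the denominator could be chosen after device events have accumulated. And the sampling margin is no defence, because random error has no direction and this error does.

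**Conclusion.** The point holds in a limited form. Followed as written, section 12.2.1 and the synopsis dilute the per-recipient frequency of device harms, in the device's favour, by f_P for procedural complications and by f_S for shocks, treated VT/VF and later device complications. For assumed shares of 1% to 10%, a true 10.0% would be shown as 9.9% to 9.0%. This rests on frequency being reported as a proportion or rate, and on unexposed subjects contributing no device events.

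A reader might infer more, and the documents do not support it:
- *That the understatement equals the whole share outside the Implant class for every outcome.* Attempted implant subjects can have procedural complications, and the 30-day limit does not rule out a later implant.
- *That the plan commits these diluted rates to a benefit-risk judgement.* Section 19.6 is a forward-looking statement that projected benefit exceeds risk. It does not say that the trial's complication rates will be weighed against benefit.
- *That the trial's main conclusions are at risk.* All-cause mortality and sudden cardiac death are unaffected, and intention to treat is right for them.

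This is a defect in the descriptive device reporting, cheap to correct and best corrected before device data accumulate.

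**What to change.** In section 12.2.1 and the synopsis, keep intention to treat for all-cause mortality and sudden cardiac death, and add a device-safety set with two denominators:
- **Procedural complications:** all S-ICD-arm subjects given anaesthesia for an implant procedure, as in footnote 2 to section 10.5. Define the set this way and not by adding the Attempted implant and Implant classes. Implant requires discharge, so a subject fully implanted who dies in hospital could fall into neither class and the worst outcome would be lost.
- **Shocks, treated VT/VF and device complications:** S-ICD-arm subjects who ever have a system in place, whenever implanted. Time at risk runs from implant to explant, death or last available device follow-up, taken as the last interrogation for shocks and episodes.

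Report the number of subjects in each section 10.5 class. Figures over all randomized to S-ICD may be shown alongside, labelled as describing the assignment strategy.

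The cost is a few lines of text and one more analysis set. The implant, out-of-service and interrogation data are already collected (Tables 11.6.3-1, 11.10.4-1 and 11.9.2-1). Reported device rates will be slightly less favourable.

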### 12.2.2. Control of Systematic Error/Bias

Selection of subjects will be made from the Investigators' usual patient load. All patients meeting the eligibility criteria and having signed the ICF will be eligible for randomization in the study.

### 12.2.3. Number of Subjects per Investigative Site

A maximum of 10% of the total number of subjects per investigative site has been established for this trial. Any one site may not enroll more than 180 subjects without written permission from the CDC.

### **12.3. Data Analyses**

Statistical tests of the difference in the primary endpoint (rate of all-cause mortality) between the randomized S-ICD and CMT groups will be computed by the unblinded statistician at periodic intervals during the trial and submitted to the Data Safety Monitoring Board (DSMB) as part of the group sequential design, and at the conclusion of the study (see section 12.1.1.3). The primary analysis will be based on statistical evaluation comparing the life-table time-to-event curves for S-ICD and CMT arms of the trial, the graphs being constructed by the method of Kaplan and Meier. The stratified log-rank test (stratified by enrolling site) will be used to evaluate statistical significance, adjusted for the group-sequential stopping rule of the trial with maximum-likelihood ordering; late-reported data will be appropriately incorporated. The hazard ratio for S-ICD relative to CMT, based on Cox proportional hazards modeling, will likewise be estimated. Also, 95% confidence limits for this hazard ratio will be determined, likewise adjusted for the sequential design.  
30

#### **12.3.1. Other Objectives/Measurements**

The secondary objective of the study will evaluate the effects of the S-ICD on all-cause mortality in various subgroups and on sudden cardiac death. Sudden cardiac death will be analyzed using methods similar to those for all-cause mortality, except that they will be performed without adjustment for the sequential design. Sudden cardiac death events in the study will be independently adjudicated by the Mortality Events Committee using the Hinkle-Thaler criteria (see Appendix 28.4).

The pre-specified subgroups include but are not limited to: gender, race, age continuous and dichotomized at 75 years, duration of diabetes, presence versus absence of insulin therapy, HbA1c < 8% or ≥ 8%, LVEF continuous and dichotomized at 40%, MADIT II risk score subgroups. For each subgroup analysis, the Cox proportional-hazards regression analysis will be used to evaluate differences between subgroups in the hazard ratios (S-ICD vs. CMT). The baseline covariate or stratum and its interaction with treatment group will be added to the regression model and a test for significant interaction carried out. Each analysis will be stratified by enrolling site, where appropriate. These analyses will be done without

adjustment for the sequential design. Subgroup analyses are further described in section 12.3.3.

Pre-specified tertiary analyses include the following:

1. Frequency and outcomes of S-ICD treated episodes of ventricular tachycardia (VT) and ventricular fibrillation (VF).
2. Frequency and outcomes of S-ICD inappropriate shocks.
3. Frequency of S-ICD device complications, including but not limited to: infection, device malfunction and electrode movement.
4. Healthcare utilization assessed through adverse event reporting.

Tertiary analyses will be descriptive and exploratory. Detailed statistical methods for these outcomes will be presented in a Statistical Analysis Plan (SAP) prior to study termination.

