### 6.2. *Secondary Study Objective*

The secondary objective of the study is to evaluate the effects of the S-ICD on all-cause mortality in various subgroups and on sudden cardiac death.

The pre-specified subgroups include but are not limited to: gender, race, age continuous and dichotomized at 75 years, duration of diabetes, presence versus absence of insulin therapy, HbA1c dichotomized at 8%, LVEF continuous and dichotomized at 40% and MADIT II risk score sub-groups (MADIT II risk score: New York Heart Association functional class > II, age > 70 years, BUN > 26 mg/dl, QRS duration > 120 ms, and atrial fibrillation).

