**11.13. *Overall Study Completion Requirements***

This study will continue to follow subjects until the sequential stopping boundary is crossed. This is estimated to include an average follow-up time of approximately 2.6 years. Once the stopping boundary has been crossed the study will be assessed to ensure adequate data has been collected. If the data safety monitoring board determines that it is appropriate to stop the trial, sites will be notified. Each subject will have a final follow-up contact and a withdrawal form to conclude their participation. For subjects withdrawn during the study, if permitted the site will contact the subjects to obtain vital status.

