### 12.1.1.3.1 Computations for Total Sample Size of 1,800 subjects

Computations show that a total sample size of  $n = 1,800$  will meet requirements (1)-(5) below (see section 28.3 for details):

- (1) Recruitment rates of 25 patients per month (ppm) in year 1, 35 ppm in year 2, and 45 ppm in years 3-4 (1800 total patients over 48 months).
- (2) A 3-year cumulative event rate of 20%, 25%, or 30% in CMT-only patients.
- (3) A 5-year cumulative drop-out rate of 10% in each arm.
- (4) A randomization ratio of 2:1, S-ICD to CMT only.
- (5) The trial should end within 6 years (2 years after recruitment ends).

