### ***12.3.7. Changes to Planned Analyses***

Any changes to the planned statistical analyses made prior to study completion will be documented in an amended Statistical Analysis Plan approved prior to implementation. Changes from the planned statistical methods after the study crossed the stopping boundary will be documented in the clinical study report along with a reason for the deviation.

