#### **27.4. Hinkle- Thaler Criteria**

##### **Clinical classification of cardiac deaths**

LE Hinkle Jr. and HT Thaler

One hundred forty-two deaths among 743 men ages 50 - 65 years who had been examined and followed 5 - 10 years were investigated and classified on the basis of clinical information from medical and non- medical observers, ECGs and autopsies. A classification based on the condition of the circulation immediately before death appears to be most relevant to studies of sudden death. In 58% of the cases, the subjects collapsed abruptly and his pulse ceased without prior circulatory collapse (arrhythmic death); in 42%, the pulse ceased only after the peripheral circulation had collapsed (deaths in circulatory failure). Thirty-three percent of arrhythmic deaths and 10% of deaths in circulatory failure occurred in a setting of clinical evidence of acute ischemic heart disease (p less than 0.005). Forty-five percent of arrhythmic deaths were preceded by chronic congestive heart failure without circulatory collapse. Ninety-three percent of final illnesses that lasted less than 1 hour ended in arrhythmic deaths; 74% lasted more than 1 day ended in deaths in circulatory failure (p less than 0.001). Eighty-eight percent of deaths that occurred outside of the hospital were arrhythmic; 71% of deaths that occurred in the hospital were deaths in circulatory failure (p less than 0.001). Ninety percent of deaths in which the primary cause of the final illness was heart disease were arrhythmic; 86% of deaths in which the primary cause was other than heart disease were deaths in circulatory failure (p less than 0.001). Ninety-one percent of deaths precipitated by an acute cardiac event were arrhythmic; 98% precipitated by acute respiratory obstruction, hemorrhage, infection, stroke or other non-cardiac events were deaths in circulatory failure (p less than 0.001).

Circulation, Vol 65, 457-464, Copyright © 1982 by American Heart Association

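### The sudden cardiac death curves make no provision for non-sudden death as a competing event, so they would modestly overstate the risk in each arm

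*Combined protocol and SAP*

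**What the plan says.** Section 6.2 sets the secondary objective: to "evaluate the effects of the S-ICD on all-cause mortality in various subgroups and on sudden cardiac death". SCD is the only cause-specific outcome named there.

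Section 12.3.1 gives the method: "Sudden cardiac death will be analyzed using methods similar to those for all-cause mortality". The only exception it states is that there is no adjustment for the sequential design. The methods referred to are in Section 12.3. There the primary analysis rests on "comparing the life-table time-to-event curves for S-ICD and CMT arms of the trial, the graphs being constructed by the method of Kaplan and Meier", with a log-rank test stratified by enrolling site for significance and a Cox model for the hazard ratio.

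Neither section mentions competing events, cumulative incidence or the handling of non-sudden deaths, and nothing elsewhere in the document does. Section 12.3.1 does promise that "Detailed statistical methods for these outcomes will be presented in a Statistical Analysis Plan (SAP) prior to study termination", but that sentence follows the list of tertiary analyses and refers to them, not to SCD. Section 12.3.7 says changes made before study completion will be "documented in an amended Statistical Analysis Plan approved prior to implementation". That is a general route for changes and commits to nothing on this point.

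**The concern.** Carrying the all-cause methods over unchanged works for the test and the hazard ratio but not for the curve. A patient who dies of heart failure or cancer can no longer die suddenly. Kaplan-Meier treats that patient as censored, that is, as someone who could still have the event later. One minus Kaplan-Meier then estimates SCD risk in a hypothetical setting without other deaths, which is higher than the proportion of patients who actually die suddenly.

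Non-sudden deaths are unlikely to be rare in diabetic, post-infarction patients aged 65 or over. What is at stake is the height of the SCD curves and any absolute risk or risk difference read from them. While non-sudden hazards are similar in the two arms, the error also enlarges the apparent absolute benefit of the device on the outcome it is meant to prevent. It is a bias, so a larger trial does not remove it.

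**Working it through.** **Inputs from the plan.**
- Control mortality: "A 3-year cumulative event rate of 20%, 25%, or 30% in CMT-only patients" (Section 12.1.1.3.1).
- All-cause hazard ratio 0.75, allocation 2:1, 1800 patients (600 control, 1200 S-ICD), maximum 454 deaths.
- Time point: the "average follow-up time of approximately 2.6 years" in Section 11.13, i.e. t = 31.2 months.

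**Assumptions.**
- Hazards are constant.
- Non-sudden deaths are censored in the SCD curve.
- The all-cause hazard ratio of 0.75 comes from SCD alone.
- The sudden share s of control deaths is 30-58%. The plan gives no share for this population. The upper value is the arrhythmic share in the cohort described in Appendix 27.4 ("In 58% of the cases, the subjects collapsed abruptly"), which is a different population.

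**The plan's own figures.** The plan states no figure for SCD. Its all-cause inputs reproduce: S-ICD 3-year mortality is 1 − 0.75^0.75 = 0.194, as stated. Recomputing the sequential design gives 453.3 events, against 453.2 in Table 12.1-1.

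**Formulas.** With r the 3-year control mortality, h = −ln(1 − r)/36 per month.
- Control: SCD hazard s·h, non-sudden hazard (1 − s)·h.
- S-ICD: non-sudden hazard (1 − s)·h, SCD hazard 0.75h − (1 − s)h. The implied SCD hazard ratio is 0.167, 0.375, 0.500 and 0.569 for s = 0.30, 0.40, 0.50 and 0.58.
- One minus Kaplan-Meier: 1 − exp(−h_SCD·t).
- Cumulative incidence: (h_SCD/h_total)·(1 − exp(−h_total·t)).

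**How many deaths are affected.** Taking person-time as proportional to allocation, the non-sudden fraction of all deaths is 3(1 − s)/2.5 = 0.84, 0.72, 0.60 and 0.50. That is 381, 327, 272 and 229 of 454.

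**Central example, r = 0.25 and s = 0.40, at 2.6 years** (h = 0.00799):

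| | 1 − Kaplan-Meier | Cumulative incidence |
|---|---|---|
| Control | 9.49% | 8.83% |
| S-ICD | 3.67% | 3.41% |
| Difference | 5.82 points | 5.42 points |
| Risk ratio | 0.387 | 0.386 |

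Consistency check in the control arm: one minus Kaplan-Meier is 9.49% for SCD and 13.89% for non-sudden death. These sum to 23.4%, but all-cause mortality at that time is only 22.1%.

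The standard error of the difference, ignoring censoring, is √(0.0883·0.9117/600 + 0.0341·0.9659/1200) = 1.27 points. The excess before rounding is 0.41 point, and 0.41/1.27 = 0.32.

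**Difference between arms across the range** (Kaplan-Meier versus cumulative incidence, points; relative excess):

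| 3-year control mortality | s = 0.30 | s = 0.40 | s = 0.50 | s = 0.58 |
|---|---|---|---|---|
| 20% | 4.67 v 4.38 (6.8%) | 4.58 v 4.33 (5.8%) | 4.50 v 4.29 (4.8%) | 4.43 v 4.26 (4.0%) |
| 25% | 5.97 v 5.48 (8.8%) | 5.82 v 5.42 (7.5%) | 5.68 v 5.35 (6.2%) | 5.57 v 5.29 (5.1%) |
| 30% | 7.32 v 6.60 (11.0%) | 7.10 v 6.50 (9.3%) | 6.88 v 6.40 (7.6%) | 6.72 v 6.32 (6.3%) |

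Within arms, the excess is 0.4-1.0 point in control and 0.1-0.6 point in S-ICD, again 4-11% in relative terms.

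**Direction.** To second order, the excess in one arm is h_SCD·h_non·t²/2. The difference between arms is therefore overstated while the SCD hazard ratio times the non-sudden hazard ratio is below about 1. Beyond that the error reverses slightly. With r = 0.25, s = 0.30, SCD hazard ratio 0.8 and non-sudden hazard ratio 1.3, the difference is 1.40 points by Kaplan-Meier and 1.42 by cumulative incidence.

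**Hazard ratio.** In 400 simulated trials of 600 versus 1200 patients with non-sudden deaths censored, the cause-specific rate ratio averaged 0.503 for a true value of 0.50.

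**The case against.** The plan says the methods will be similar, not identical. It does not state that non-sudden deaths are censored, and it promises no SCD percentages. An Aalen-Johansen curve with a cause-specific log-rank test would fit that wording. Significance rests on the log-rank test and the effect measure is the hazard ratio, and both are sound. The effect is small and rests on assumptions that favour the concern: giving SCD the whole benefit implies an SCD hazard ratio as low as 0.167. Under milder effects at 25% mortality and a 30-40% share, the excess in the difference is 0.29-0.32 point (SCD hazard ratio 0.5, non-sudden 1.0) or 0.25-0.28 point (0.75 for both). These are about 0.25 and 0.2 of a standard error. The matter could also be settled later from deaths that are adjudicated anyway.

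Most of this stands as a limit on size, and the test and hazard ratio are not in dispute. It does not remove the gap. The wording permits the right estimator but does not commit to it, and the one stated exception is a different matter. The excess also grows along the curve: in the central example at 60 months the difference is 10.5 versus 9.2 points. Little weight belongs there, however. By Table 27.3-1, 545 patients are enrolled by month 19 and could reach 60 months of follow-up if the trial runs to month 79, but only 50 could if it ends at month 62, the expected duration in Table 12.1-4.

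**Conclusion.** The concern holds. On its natural reading the plan would draw SCD curves that are too high in each arm, by 4-11% in relative terms at 2.6 years. The difference between arms would be overstated by the same proportion, or 0.2-0.7 point. This rests on constant hazards, censoring of non-sudden deaths, an assumed sudden share of 30-58% and equal non-sudden hazards in the two arms. The risk ratio barely moves. The primary endpoint, type I error, power, SCD test and SCD hazard ratio are unaffected. The error is modest and confined to the curves of a secondary outcome, but it should be corrected because a better estimator is available at almost no cost.

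**What to change.** In Section 12.3.1, or in the SAP before results by arm are known:

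- Replace Kaplan-Meier for SCD with Aalen-Johansen cumulative incidence curves by arm, with non-sudden death as the competing event.
- Label the site-stratified log-rank test and the Cox hazard ratio for SCD as cause-specific.
- Report non-sudden death by arm in the same way. This also shows whether the non-sudden hazards differ, which decides the direction of any error in the difference.

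Optionally, add a sensitivity analysis that counts as sudden the deaths the Mortality Events Committee cannot classify (Appendix 27.2).

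The cost is wording. All deaths already go to the committee, so no new data, no change to adjudication and no change to the primary analysis are needed.
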